9.3.3.4 Cumulative Trial Strategy Related Radiation Exposure

Radiation exposure for diagnostic and procedural testing will be collected for each participant and the average accumulated radiation dose for 1 year, in millisievert (mSV) units, will be calculated. This calculation will be known as the cumulative radiation exposure. For cath, PCI, CTA, and stress nuclear, the missing values will be imputed based on the distribution of data from trial participants with complete radiation information. If data are missing in > 80% or more of the diagnostic and procedural testing, a single fixed estimate of radiation based on the literature will be used to impute.

Table 3. Radiation Estimates for Imputation

Procedure	Imputation Result
CTA (Stocker 2018)	5.1 mSv*
Stress Nuclear Imaging (Mieres 2014)	11mSv Rest or Rejection Sestamibi (Cardiolite) 3mSv Stress Sestamibi (Cardiolite) 11mSv Rest or Rejection Tetrofosmin (Myoview) 3mSv Stress Tetrofosmin (Myoview) 22mSv Thallium 3mSv Rubidium 2.0mSv 13N-ammonia
Cardiac Catheterization (Lu 2017)	7 (mSv)
Cardiac Catheterization with PCI (Lu 2017)	15 (mSv)

* 195 mGy/cm, calculated with conversion factor 0.026 mSv/mGy*cm (Stocker 2018), (Trattner 2018), and (Carpeggiani 2017)]

Conversion factor from MBq to mSv (ICRP 2007)

- Rest Tc sestamibi 9.0×10^{-3} mSv/MBq
- Stress Tc sestamibi 7.9×10^{-3} mSv/MBq
- Rest Tc tetrofosmin 6.9×10^{-3} mSv/MBq
- Stress Tc tetrofosmin 6.9×10^{-3} mSv/MBq
- Rb 3.4×10^{-3} mSv/MBq

- N ammonia 2.0×10^{-3} mSv/MBq

For exposure observed in this study, data will be summarized using descriptive statistics (mean [SD], median [25th, 75th percentiles], min and max). To compare the radiation exposure distributions between the precision care arm and the usual care arm, a waterfall plot of cumulative radiation exposure will be constructed. Comparison between 2 groups will be conducted using a non-parametric approach such as Wilcoxon rank-sum test. The analysis will be repeated for 2 populations: 1) low risk participants only and 2) elevated risk or known atherosclerosis participants only. The radiation exposure for diagnostic test sources will be summarized descriptively.

9.3.3.5 Revascularization

Coronary revascularization procedures (CABG surgery and PCI) performed will be collected during the follow-up. The number (%) and proportion of catheterizations leading to revascularization will be summarized and compared between the precision care arm and usual care arm. Coronary revascularization procedures determined to be ischemia driven will be summarized descriptively. Similarly, for the invasive coronary angiogram participants the number (%) of revascularizations performed in the first 6 months post catheterization will be summarized in each arm.

9.3.3.6 Prevention Motivation

Prevention motivation information will be assessed at study entry and during the participant follow-up at 45 days, 6 months and 12 months. Specifically, this includes an assessment of the importance of cardiac risk prevention to the participant's future health (5 point Likert scale from not important>>>very important) at baseline, 45 days and 12 months, as well as an assessment of whether the PRECISE evaluation changed the participant's motivation to modify cardiac risk factors and improve heart health, and an inquiry regarding how their testing results were communicated by their healthcare provider (asked at 45 days and 12 months). The number (%) will be summarized between the precision care arm and usual care arm and compared using Pearson's chi-square test at entry, 45 days and 12 months.

1. Participants will be characterized by reported cardiac risk prevention importance at baseline and post evaluation at 45 days and 12 months by randomized arm, testing received, and testing results
2. Among participants receiving testing by 45 days, will be characterized by response at 45 days by randomized arm, testing received, and testing results as having:
 1. Increased my motivation
 2. Did not change my motivation
 3. Decreased my motivation
 4. I don't know the results of my evaluation
3. Among those tested by 45 days and who received test results, method of communication of testing results will be characterized by response at 45 days by randomized arm, testing received, and testing results
4. Among those who received test results, association of the method of communication (method of sharing test results) reported at 45 days and reported change in motivation overall and by test results

5. The association of medication use (antiplatelet usage, lipid lowering medication usage, and anti-hypertensive medication usage) and change in motivation responses (increase, decrease no change, did not receive) and rates of medication use (aspirin/anti-platelet agents and statins) at 45 days and 12 months

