Sample size and power calculations for this study are based on the hypothesis that the precision evaluation arm is superior to the usual care arm on the time-to-first event of the composite 3-component endpoint: all-cause death, non-fatal MI, or invasive cardiac catheterization without obstructive CAD (obstructive CAD defined as diameter stenosis $\geq 50\%$, FFR ≤ 0.80 , or iFR ≤ 0.89) over a 12-month of follow-up. Time to event analysis will use the date of the event, including the date of catheterization at which the absence of obstructive CAD is demonstrated. Assuming 10% of usual care participants will receive angiography as a first test results in an 8% primary endpoint event rate at 1 year in the usual care group and 5% event rate in the precision care group (i.e., 3% absolute [37.5% relative] effect size). Assumptions used in the primary endpoint event rate calculations (i.e., 8% vs. 5%) were: overall 10% will not receive randomized evaluation, and within the precision evaluation arm, approximately 20% will be assigned to guideline-recommended care with symptom management and no planned testing, of whom about 30% will have escalation of care to cCTA with selective FFRCT.

Randomizing 1050 participants per group (2100 total participants) is estimated to provide at least 90% power to detect a relative risk reduction of 37.5% in the precision evaluation arm (see Table 1 below, or refer to the power curves in the protocol). Sample size/power calculations are based on the log-rank test with 12-month accrual period, a minimum 12-month follow-up (i.e. last participant will be followed for at least 12-months), 10% attrition rate (i.e. lost to follow-up, dropouts) and a two-sided type I error rate of 0.05.

The DSMB will review interim analysis data for efficacy as well as possible sample size re-estimation. At any interim analyses, the O'Brien-Fleming boundary generated by Lan-DeMets alpha-spending function will be utilized as a statistical stopping rule (See DSMB charter for more details).

Table 1. The total number of participants needed for 85%, 90%, and 95% power. Although this is not an event-driven study, the table below also provides total number of MACE needed.

1-year event rate in precision evaluation arm	Power	Total number of Primary Events needed	Total number of participants needed
(37.5% ^{2%} effect size)	85%	173	1792
	90%	202	2096
	95%	250	2592

8. Database Sources

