9.1 General Approach

Continuous variables will be summarized as means (standard deviations), medians (25th and 75th percentiles), minimum and maximum. Number (percentage) of participants in each category will be presented for categorical variables. Comparisons of categorical variables between the two randomized arms or between pre-specified subgroups will be performed using Pearson's chi-square test or Fisher's exact test depending on expected cell sizes; comparisons of continuous variables will be performed using the Wilcoxon rank-sum test.

Unless otherwise stated, all hypothesis tests will be performed using two-sided tests. No adjustment for multiplicity is planned.

All primary statistical analyses will be conducted using the intention-to-treat principle to define treatment assignment, except as indicated.

In addition to the pre-specified subgroup analyses (see Section 9.4), response magnitude analyses may be considered, in which participants are evaluated based on a binary variable indicating improvement or no improvement with respect to a given assessment.

[figure not shown]
Analyses will be performed using SAS software version 9.4 or higher (SAS Institute, Inc., Cary, NC).

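### SAP 9.3.3.6 tests an ordered 5-point importance-of-prevention item, which has a baseline answer, with Pearson's chi-square, which uses neither the order nor the baseline

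*SAP*

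**What the plan says.** SAP 9.3.3.6 (Prevention Motivation) describes three items. The first rates the importance of cardiac risk prevention on a "5 point Likert scale from not important>>>very important" and is asked at baseline, 45 days and 12 months. The other two, on change in motivation and on how test results were communicated, are asked only at 45 days and 12 months.

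One sentence sets the analysis for all three: numbers and percentages by arm, "compared using Pearson's chi-square test at entry, 45 days and 12 months". Because only the importance item is asked at entry, that test must cover the ordered scale.

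This follows the general rule in SAP 9.1: "Comparisons of categorical variables between the two randomized arms or between pre-specified subgroups will be performed using Pearson's chi-square test or Fisher's exact test". The rank test named in the same section is reserved for other data: "comparisons of continuous variables will be performed using the Wilcoxon rank-sum test". Section 9.1 names no method for ordered categories. The tables planned for this item in SAP section 10 (2.10, 4.11.1.1 and 4.11.1.2) list no ordinal or baseline-adjusted comparison. By contrast, SAP 9.3.2 enters the baseline score as a covariate for the quality-of-life scales.

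**The concern.** Permuting the five answer labels leaves Pearson's statistic unchanged. A consistent move towards the top of the scale therefore earns no more weight than an unordered reshuffling of the same size. The test has no direction and produces no effect estimate with an interval. The baseline answer is only compared between randomized arms, where any difference is due to chance. It is not used to sharpen the follow-up comparison.

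The item asks how much prevention matters to the participant, so a difference between arms is most useful if it can be read as more or less. What is at stake is efficiency and readability of one additional analysis. Type I error is not at issue: it stays near 5% for both Pearson and Wilcoxon in simulation.

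**Working it through.** The plan states no power, effect size or expected distribution for this item, so there is no figure of its own to reproduce.

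**Inputs from the documents**
- Five ordered categories, two arms: Pearson has (2 − 1) × (5 − 1) = 4 df.
- 1050 per arm and 10% attrition (SAP section 7): 1050 × 0.90 = 945 per arm. This is borrowed, because no completeness is stated for this item.
- "Unless otherwise stated, all hypothesis tests will be performed using two-sided tests" (SAP 9.1). The 0.05 level is the one given for the sample size in SAP section 7, assumed to apply here.

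**Assumed**
- A proportional-odds shift.
- Three usual-care answer distributions, lowest to highest category: A (1, 2, 7, 25, 65)%, B (3, 7, 20, 35, 35)%, C (10, 15, 25, 25, 25)%.

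**Step 1: cost of ignoring order.** An ordinal 1-df test with power P has noncentrality λ = (1.96 + z_P)². For P = 80%, λ = (1.96 + 0.842)² = 7.85. The same λ on 4 df gives Pearson's power.

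| Ordinal test, 1 df | Pearson, 4 df | Loss (points) |
|---|---|---|
| 50% | 30.8% | 19 |
| 60% | 38.9% | 21 |
| 70% | 48.2% | 22 |
| 80% | 59.5% | 20.5 |
| 90% | 74.0% | 16 |
| 95% | 83.7% | 11 |
| 99% | 94.8% | 4 |

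**Step 2: check on explicit distributions, n = 945 per arm.** Let p and q be the usual-care and precision-care proportions, p̄ their mean, and r the midranks from p̄.
- Pearson: λ = n Σ[(p − p̄)² + (q − p̄)²]/p̄, on 4 df.
- Wilcoxon: λ = n[Σ(q − p)r]²/(2 Var r), on 1 df.

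Example: B with odds ratio 1.25 gives q ≈ (2.4, 5.7, 17.4, 34.2, 40.2)%. Both λ are 7.02, so Pearson has 54.2% and Wilcoxon 75.5%.

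| Odds ratio | A: Pearson / Wilcoxon | B | C | Gap (points) |
|---|---|---|---|---|
| 1.1 | 10.5 / 17.0% | 12.4 / 20.6% | 12.8 / 21.4% | 6–9 |
| 1.25 | 42.0 / 63.5% | 54.2 / 75.5% | 56.6 / 77.6% | 21–22 |
| 1.3 | 55.9 / 77.0% | 70.0 / 87.5% | 72.6 / 89.1% | 17–21 |
| 1.4 | 79.4 / 92.9% | 90.9 / 97.8% | 92.4 / 98.3% | 6–14 |
| 1.5 | 92.6 / 98.4% | 98.2 / 99.8% | 98.7 / 99.8% | 1–6 |

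A separate simulation of 10,000 trials (945 per arm, odds ratio 1.28, a high-skewed distribution) gave Wilcoxon 80.4% and Pearson 59.2%.

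**Step 3: cost of ignoring baseline.** If adjustment multiplies the variance by 1 − ρ², then λ becomes λ/(1 − ρ²). Starting from an ordinal test with 80% power:
- ρ = 0.3: 7.85/0.91 = 8.63, power 83.6%
- ρ = 0.5: 7.85/0.75 = 10.47, power 89.9%
- ρ = 0.7: 7.85/0.51 = 15.39, power 97.5%

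Simulated rank ANCOVA with latent correlation 0.3 to 0.5 gave smaller gains, about 2 to 7 points. The documents give no value for ρ.

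**Step 4: where the ranking reverses.** Under one assumed polarising shift, with both ends of the scale gaining, Pearson had 99.9% power and Wilcoxon 39.2%.

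**The case against.** Much of the case for the plan as written stands.

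- **The method is valid and consistent with the SAP.** Section 9.1 sends categorical variables to Pearson or Fisher, and 9.3.3.6 follows it. The Wilcoxon rule covers continuous variables and does not make Pearson an error.
- **The item is peripheral.** Prevention motivation is not among the endpoints in SAP 4.1 to 4.1.2, and its follow-up tables are titled as descriptive summaries. No hypothesis or power target is attached to it. Even so, 9.3.3.6 does prespecify a test.
- **Direction is partly visible.** The n (%) table shows which categories moved. SAP 9.1 also allows an optional improved / not improved analysis, but that discards further information and is not committed to.

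Four stronger readings are tempting and not supported:

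1. *A fixed loss of 20 points.* That is close to the worst case. Step 2 gives 1 to 14 points at odds ratios 1.1, 1.4 and 1.5, and nothing in the documents says which effect to expect.
2. *20 points for order and baseline together.* The figure comes from order alone.
3. *A particular threat to participants assigned to no testing.* The power figures describe all randomized participants. About 20% of the precision arm is expected to be assigned to no testing (SAP section 7), or 0.20 × 1050 = 210 people. With about 190 per arm and odds ratio 1.25, Pearson has 11–14% and Wilcoxon 18–23%; neither test is adequate.
4. *The same remedy for the change-in-motivation item.* That item is analysed among participants tested by 45 days and has a don't-know answer, so it raises separate questions.

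**Conclusion.** The point holds as a modest one. For the importance item, the planned test uses neither the order of the answers nor the baseline response, and no other section of the SAP supplies a comparison that does.

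Under an assumed proportional-odds shift, ignoring order costs about 16 to 22 points of power when an ordinal test would have 50% to 90%. Outside that range the loss shrinks, and a polarising change can favour Pearson. Ignoring baseline adds a loss whose size rests on an unknown correlation. The effect sizes, answer distributions, correlations and the 945 per arm with data are all assumptions for this item.

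Severity is low: this is an additional analysis, and no conclusion about the primary or listed secondary endpoints depends on it.

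**What to change.** In SAP 9.3.3.6, for the importance item at 45 days and 12 months, replace Pearson's chi-square with a proportional-odds model containing arm and baseline answer. A van Elteren (stratified Wilcoxon) test with baseline answer as the stratum is an acceptable alternative for the test. Report the common odds ratio with its 95% CI, and keep the n (%) table beside it so that a non-monotone pattern stays visible. Summarise the entry values descriptively, without a test. Keep Pearson for the communication-method item, whose categories are unordered.

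The cost is a change of wording and one model, with no new data. There are two small downsides. The odds ratio is a summary under proportional odds, although the rank test remains valid without that assumption. A 1-df test is also less sensitive than Pearson to a non-monotone change.

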Participants randomized to the precision evaluation arm will be assigned a management approach based on their PROMISE Risk Score, a risk model based on pre-test clinical characteristics derived from the PROMISE trial and validated in SCOT-HEART³⁴ or the presence of known non- obstructive atherosclerosis. Participants will be assigned to either 1) guideline-recommended medical management without planned testing (low risk) or 2) cCTA with selective FFR_{CT} (elevated risk or those with known plaque, independent of the PROMISE Risk Tool assessment). Participants assigned to the strategy of guideline-recommended medical management without planned testing will be treated with risk-appropriate preventive care and symptom control (including therapeutic trials of anti-anginal medications). Participants and their providers will be provided informational materials demonstrating the safety of this strategy based on pre-test probabilities and the PROMISE Risk Score. Participants with intractable symptoms despite maximal medical management whose clinicians opt for further testing (crossovers) will undergo cCTA with selective FFR_{CT}.

Participants undergoing cCTA as the initial test (both assigned or crossover) should have FFR_{CT} analysis ordered if cCTA shows at least one 30-90% stenosis in epicardial vessels of 2mm diameter or greater. Image sets will be sent promptly to HeartFlow for analysis and results will be returned to sites in < 24 hours to enable rapid incorporation into clinical decision making.

V.D. Participant Follow-Up

Participants will be followed up at 45 (+/-14) days and at 6 and 12 months (+/- 30 days) after enrollment. For US participants, follow-up at 45 days and at 6 and 12 months will be done by phone interviews conducted by the DCRI Outcomes Call Center, unless not allowed by their enrolling site. For participants outside of the US, follow-up will be conducted by the site coordinators.

Activities to be conducted at each follow up contact are described below and in the Schedule of Events.

45 (+/-14) day follow-up visit (in-person, portions may be done by phone) At the 45-day follow-up visit, participants will be asked the following:

- Assessment if any MACE has occurred since enrollment

- CV Update: Review and documentation of any cardiovascular diagnostic test, cardiovascular procedure, or hospitalizations/clinic visits due to cardiovascular symptoms and complications since enrollment

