In accordance with the Declaration of Helsinki, each participant is free to withdraw from the study at any time. Investigator(s) also have the right to withdraw participants from the study in the event of illness or other reasons concerning the health or wellbeing of the participant, or in the case of lack of cooperation. Should a participant decide to withdraw or should the investigator(s) decide to withdraw the participant, all efforts will be made to complete and report the observations up to the time of withdrawal as thoroughly as possible. If possible, a complete final evaluation at the time of the participant's withdrawal should be made. The reason for withdrawal must be noted in the eCRFs.

V.G. Schedule of Assessments

	Screening	Randomization Day 1	Day 45 (+/- 14 d)	6-mo. (+/- 30d)	12-mo. (+/- 30d)
Informed consent	X				
Medical history	X				
Cardiovascular update ¹			X	X	X
Concomitant cardiovascular medications	X		X	X	X
Cardiovascular risk factors (including PROMISE minimal risk score data entry for randomization)	X				
² Pregnancy test	X				
³ Creatinine	X				
⁴ Resting 12-lead ECG	X				
QoL evaluation: SAQ, EQ5D-5L	X		X	X	X
Participant Satisfaction Questionnaire			X		
Randomization		X			
Initial diagnostic invasive or noninvasive test performed (if assigned)		Prior to 45 day visit			
Cardiac imaging/testing clinical report and image collection			X	X	X
Interval assessment for CV events and testing			X	X	X
Endpoint assessments			X	X	X

1. During cardiovascular update, if participants have received an additional diagnostic test, a cardiovascular procedure or have been hospitalized since the last visit, additional data will be collected
2. For a female participant of childbearing potential, a pregnancy test must be performed with negative results known within 7 days prior to randomization
3. Creatinine blood draw required only for participants without a recent normal value (most recent within previous 90 days)
4. Resting 12-lead ECG preferred in last 30 days (optional, clinical care only)

VI. ADDITIONAL ASSESSMENTS AND SUBSTUDIES

VI.A. Quality of Life Assessments

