10.	Planned Table of Contents for Analysis Tables and Figures.....	24
11.	Changes from the Protocol	27
12.	References	28
Appendix I.	Schedule of Activities.....	30

[figure not shown]
1. Study Title

Prospective Randomized Trial of the Optimal Evaluation of Cardiac Symptoms and Revascularization (PRECISE).

2. Study Design

The study is a prospective, pragmatic, randomized clinical trial of the comparative effectiveness of diagnostic evaluation strategies for suspected stable CAD, performed in outpatient settings. Qualifying patients are those presenting with new symptoms suspicious for clinically significant CAD (and without known obstructive CAD), who are recommended for diagnostic testing and have not received any testing for cardiovascular ischemia with the past 12 months. Patients meeting these criteria will be randomized to an initial strategy of either precision care or usual care. The Usual Care Arm requires initial testing in all participants using either noninvasive testing (of the site's choice, including stress nuclear, stress echocardiography, stress MRI, or exercise ECG) or invasive testing (invasive coronary angiography) according to the pre-randomization intended testing strata. cCTA and calcium scoring are prohibited as a subsequent test for the first 45 days after randomization. Participants randomized to the Precision Evaluation Arm will be assigned to either no immediately planned testing, if Low Risk (see derivation below), or cCTA with selective FFR_{CT} if Elevated Risk or with known non obstructive atherosclerosis. If Low Risk participants develop a need for testing, such increasing angina, cCTA with selective FFR_{CT} must be used. All subsequent decisions in the usual care arm regarding additional testing, medications, and/or procedures are at the discretion of the responsible clinical care team.

See Figure 1 for a description of the participant flow.

Figure 1. Participant flow in the study.

3. Objectives

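### The by-arm motivation comparison in SAP 9.3.3.6 is limited to tested participants, so its arm totals differ in risk mix by design

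*SAP*

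**What the plan says.** SAP 9.3.3.6 plans three kinds of motivation output. Item 1 is a rating of how important cardiac risk prevention is, at baseline, 45 days and 12 months, and is not limited to tested participants. Item 2 asks whether the evaluation changed motivation, and is limited as follows: "Among participants receiving testing by 45 days, will be characterized by response at 45 days by randomized arm". Item 3 asks how results were communicated, among those tested by 45 days who also received results. The section states that arms will be compared by Pearson's "chi-square test at entry, 45 days and 12 months". It names no stratification or adjustment.

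Two statements in SAP section 2 determine who can enter the tested group. On one side, "The Usual Care Arm requires initial testing in all participants". On the other, "Participants randomized to the Precision Evaluation Arm will be assigned to either no immediately planned testing, if Low Risk". SAP section 7 expects that "approximately 20% will be assigned to guideline-recommended care with symptom management and no planned testing, of whom about 30" per cent will escalate to cCTA, and that 10% overall will not receive their randomized evaluation.

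On timing, Protocol V.D states: "Participants will be followed up at 45 (+/-14) days and at 6 and 12 months (+/- 30 days) after enrollment". The Schedule of Assessments (Protocol V.G) places the initial test "Prior to 45 day visit".

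**The concern.** The analysis group for items 2 and 3 is formed after randomization, by an event that the randomized strategy itself controls. Most low-risk precision participants leave the group and most low-risk usual-care participants stay. The two arm totals are then no longer the randomized groups: one is almost entirely elevated risk and the other is about one-fifth low risk. If motivation after an evaluation depends on risk level, a chi-square on the totals mixes that dependence with any effect of the strategy. A reader could credit the precision strategy with a difference that the choice of denominator produced, or miss a real one that it cancelled.

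**Working it through.** The documents give no sample size, power or alpha for this analysis, so there is no figure of the plan's own to reproduce. The check derives the expected make-up of the tested groups and what follows from it.

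**Inputs** (SAP section 7): 1050 per arm; 20% low risk; 30% of low-risk precision participants escalate; 10% do not receive their evaluation. The time of escalation is not given, so the share escalated by day 45 is taken as 0 to 30%. The 10% is applied to assigned tests. All tests received are taken as done by day 45, and all tested participants as answering.

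**Make-up of the tested groups**
- Usual care: 1050 × 0.9 = 945 tested, of whom 945 × 0.20 = 189 (20%) are low risk.
- Precision, elevated risk: 1050 × 0.8 × 0.9 = 756.
- Precision, low risk: 1050 × 0.2 × (0 to 0.3) = 0 to 63.
- Precision total: 756 to 819, of whom 0/756 = 0% to 63/819 = 7.7% are low risk.
- Imbalance in low-risk share: 20 − 7.7 = 12.3 points, up to 20 points.
- Low-risk precision participants outside the group: 210 − 63 = 147, up to 210. In usual care about 10% of low-risk participants are lost.

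**Arm difference from risk mix alone**

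Difference = imbalance × (low-risk minus elevated-risk response). The response gap is an assumption; the documents give none.
- Gap of 10 points: 0.123 × 10 = 1.2, up to 0.20 × 10 = 2.0 points.
- Gap of 20 points: 0.123 × 20 = 2.5, up to 0.20 × 20 = 4.0 points.

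**Effect on a nominal 5% test when the strategy has no effect**

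Further assumption: 40% of elevated-risk participants report increased motivation, low-risk participants report more, and the answer is treated as two categories. Rejection probability = Φ((d − 1.96·SE0)/SE1) plus the opposite tail, where SE0 uses the pooled proportion and SE1 the separate ones. For a 20-point gap and no escalation, the proportions are 0.44 (n = 945) and 0.40 (n = 756), d = 0.04, SE0 = 0.0241 and SE1 = 0.0240. The rejection probability is about 38%.

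| Low-risk share | Gap 10 points | Gap 20 points |
|---|---|---|
| 10% | 6–7% | 9–14% |
| 20% (SAP) | 8–13% | 18–38% |
| 30% | 11–22% | 30–67% |

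Each range runs from 30% escalated by day 45 (lower figure) to none (higher figure).

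**Timing**

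The contact window is 45 ± 14, that is days 31 to 59. If the schedule is kept, no answer precedes an assigned test. If it is not, the share of answers given before a test that still falls by day 45 depends on assumed spreads. With contacts uniform over days 31 to 59, it is about 8% for tests uniform over days 1 to 45, about 12% for days 15 to 45, and 0% if all tests are done by day 30. In the other direction, a participant tested on day 50 and contacted on day 58 keeps the schedule, but is dropped if 45 days means the calendar day.

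**The case against.** The strongest reply is that the chi-square may not be meant for items 2 and 3. The time points named for it include entry, which fits the importance rating and cannot fit a question about the effect of the evaluation. Items 2 and 3 are worded as characterization by arm, testing received and results. It is also reasonable to put a question about test results only to people who were tested, and Tables 4.11.2 and 4.11.4 are openly titled as-tested. The column convention in SAP section 10 splits usual care into low and elevated risk and precision into no testing and CTA, so a like-for-like pair can be read. Item 1 already covers all participants.

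Much of this stands. The text is ambiguous about which items are tested, and the section 10 columns help descriptive reading. They do not stratify a test of the arm totals, however, and the section names no other between-arm test. The SAP does take this step elsewhere: the radiation comparison in 9.3.3.4 is repeated within each risk group.

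A reader might also infer that some motivation answers are given before the test. The documents do not show this. The schedule puts the assigned test before the visit, and 45 days can be read as the visit label in both halves of item 2. Item 3 requires results already received. Item 2 also offers "I don't know the results of my evaluation", although that option does not separate the not-yet-tested from those tested without results.

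Nor are low-risk precision participants simply untested: they have no immediately planned test, and some are expected to escalate.

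**Conclusion.** The point holds for comparability. On the SAP's own assumptions, the tested groups would be about 20% low risk in usual care and 0 to 7.7% in precision, so a difference between arm totals can reflect risk mix and not strategy. The make-up follows from SAP section 7, apart from the unknown timing of escalation. The 1.2 to 4 point distortion and the rejection rates rest on response differences assumed here, and would vanish if low- and elevated-risk participants answered alike.

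The timing issue is only a gap in definition: the SAP does not tie the test date to the contact date. It would be too strong to say that the section cannot inform on the strategy at all, because item 1 is open to every participant. Priority is low, since prevention motivation is absent from the primary, secondary and additional endpoints in SAP sections 4.1 to 4.1.2.

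**What to change.** In SAP 9.3.3.6:
- Make any by-arm test of items 2 and 3 within the elevated-risk or known-atherosclerosis randomization stratum, where both arms are assigned a test (about 756 versus 756).
- Describe low-risk tested participants separately, without an arm test.
- For the whole-strategy comparison, use the item 1 importance rating in all randomized participants, adjusted for baseline.
- Define tested by 45 days as a first test dated before that participant's actual 45-day contact.

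The cost is SAP wording and one date flag, with no new data collection. The by-arm test loses 189 usual-care and 0 to 63 precision participants, that is 189/1701 = 11% to 252/1764 = 14% of the tested total. Restricting to tested participants within the stratum is still a post-randomization choice, so if non-receipt of the assigned test differs between arms some imbalance could remain. The number not tested should be shown by arm.
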